10.1.7 General remarks - important!

Because of lacking analytical coverage beyond the instructed preparation procedure of the different dose formulations, no further (external) dilutions of the reconstituted solutions are allowed!

The present Reconstitution Instruction does not contain any advice how to withdraw a specific dose from the reconstituted solutions. The specific dose volumes to be withdrawn from the described dose formulations in order to obtain a required dose will be calculated and documented by TransMed in the Clinical Trial Protocol (CTP) and subsequent documents (e.g. work sheets)!

## 2. LIST OF ABBREVIATIONS

Term	Definition / description
██████████	██████████
AE	Adverse event
AESI	Adverse event of special interest
ANOVA	Analysis of variance
██████████	██████████
██████████	██████████
AUC 0-tz	Area under the concentration-time curve of the analyte in plasma over the time interval from 0 to the time of the last quantifiable data point
██████████	██████████
AE	Adverse Event
BI	Boehringer Ingelheim
BMI	Body mass index
██████████	██████████
CARE	Clinical data Analysis and Reporting Environment
CDR	Clinical Data Repository
CI	Confidence interval
██████████	██████████
C max	Maximum measured concentration of the analyte in plasma
CV	Arithmetic coefficient of variation
CTP	Clinical Trial Protocol
CTR	Clinical Trial Report
DILI	Drug induced liver injury
ECG	Electrocardiogram
EMA	European Medicines Agency
EOT	End of trial
gCV	Geometric coefficient of variation
gMean	Geometric mean
ICH	International Conference On Harmonisation
ISF	Investigator site file

Term	Definition / description
LLT	Lowest level term
log	Natural logarithm
Max	Maximum
Mean	Arithmetic mean
MedDRA	Medical Dictionary For Regulatory Activities
Min	Minimum
N	Number of non-missing observations
O*C	Oracle Clinical
PK	Pharmacokinetics
PKS	PK analysis set
PV	Protocol Violation
R	Reference treatment
RAGE	Report Appendix Generator system
REP	Residual effect period
RPM/DBLM	Report planning and database lock meeting
RS	Randomised set
SD	Standard Deviation
SDL	Subject data listing
T	Test treatment
TS	Treated set
TSAP	Trial Statistical Analysis Plan
ULN	Upper limit of normal
WHO-DD	World Health Organisation – Drug Dictionary

### **3. INTRODUCTION**

As per ICH E9 ([1](#)), the purpose of this document is to provide a more technical and detailed elaboration of the principal features of the analysis described in the protocol, and to include detailed procedures for executing the statistical analysis of the primary and secondary variables and other data.

This TSAP assumes familiarity with the Clinical Trial Protocol (CTP), including Protocol Amendments. In particular, the TSAP is based on the planned analysis specification as written in CTP Section 7 “Statistical Methods and Determination of Sample Size”. Therefore, TSAP readers may consult the CTP for more background information on the study, e.g., on study objectives, study design and population, treatments, definition of measurements and variables, planning of sample size, randomization.”

Study data will be stored in a trial database within the Oracle ClinicalTM (O\*C) system. Laboratory data will additionally be loaded and stored in the CDR.

The statistical analyses will be performed within the validated working environment CARE (Clinical data Analysis and Reporting Environment), including SASTM (Version 9.4, by SAS Institute Inc., Cary, NC, USA), and a number of SASTM-based tools (e.g., macros for the analyses of adverse event (AE) data or laboratory data; Report Appendix Generator system (RAGe) for compilation/formatting of the clinical trial report (CTR) appendices).

Pharmacokinetic (PK) parameters will be calculated using Phoenix WinNonlinTM software (version 6.3, Certara USA Inc., Princeton, NJ, USA).

#### **4. CHANGES IN THE PLANNED ANALYSIS OF THE STUDY**

All analyses described in this TSAP are in accordance with the statistical methods described in the CTP version 1.0.

## **5. ENDPOINTS**

The endpoints will be as defined in the CTP.

### **5.1 PRIMARY ENDPOINTS**

The following primary pharmacokinetic endpoints given in the CTP in Section 5.5.1.1 will be determined for BI 1467335:

- $AUC_{0-tz}$  (*area under the concentration-time curve of the analyte in plasma over the time interval from 0 to the last quantifiable data point*)
- $C_{max}$  (*maximum measured concentration of the analyte in plasma*)

[figure not shown]
### **5.2 SECONDARY ENDPOINT(S)**

#### **5.2.1 Key secondary endpoint(s)**

Not applicable as no key secondary endpoints have been specified in the protocol.

#### **5.2.2 Secondary endpoint(s)**

Not applicable as no secondary endpoints have been specified in the protocol.

### **5.3.2 Safety endpoints**

#### **General**

The following safety assessments will be evaluated as further endpoints (see CTP, Section 5.2.1):

- AEs (including clinically relevant findings from physical examination)
- Safety laboratory tests
- 12-lead ECG (abnormal findings documented as AEs or baseline conditions)
- Vital signs (systolic and diastolic blood pressure, pulse rate)

## **6. GENERAL ANALYSIS DEFINITIONS**

### **6.1 TREATMENT(S)**

For basic study information on treatments to be administered, assignments of treatment groups, and selection of doses, see CTP Section 4. Subjects will be randomly allocated to one of 3 treatment sequences (ABC, BCA and CAB). The study has a single dose, randomised, three-way crossover, open-label design.

Subjects will be randomized to one of the 3 treatment sequences. Treatments to be evaluated are outlined in [Table 6.1: 1](#) below.

Table 6.1: 1 Treatment regimens

Description of treatment regimen	Label	Short Label
BI 1467335, 2*5mg tablet, po, qd, fasted	A	BI 10 mg tab, fasted
BI 1467335, 0.5 mg/mL solution, 10mg, po, qd, fasted	B	BI 10 mg sol, fasted
BI 1467335, 2*5mg tablet, po, qd, fed	C	BI 10 mg tab, fed

tab= tablet, sol= solution

**CTP (Section 6.2.2 Treatment periods):** *Each subject is expected to participate in each of the three treatment periods (drug administration on Day 1 of each period, see [CTP] Table 4.1.4:1). Treatment periods will be separated by at least 21 days between drug administrations.*

*On Day -1 of each treatment period, study participants will be admitted to the trial site and kept under close medical surveillance for at least 24 h following drug administration on Day 1. Subjects will then be allowed to leave the trial site after formal assessment and confirmation of their fitness. Within the time window Day -5 to -1 of Visits 3 and 4, safety laboratory will be taken and AE/ concomitant questioning will be done.*

*For details on time points and procedures for collection of plasma samples for PK analysis, refer to Flow Chart and [CTP] Sections 5.5.2 and 5.6.3.*

*The safety measurements performed during the treatment period are specified in [CTP] Section 5.2 of this protocol and in the Flow Chart. For details on time points for all other trial procedures, see Flow Chart. AEs and concomitant therapy will be assessed continuously from screening until the end of trial examination.*

For the statistical analyses of AEs, laboratory data and vital signs, the following phases of the study will be defined:

Table 6.1: 2 Study phases

Label	Start	End*
Screening	Date of informed consent	Date/time of first drug administration
BI 10mg tab fasted or BI 10mg sol fasted or BI 10mg tab fed	Date/time of BI 1467335 administration	Date/time of BI 1467335 administration [REDACTED] days
F/U BI 10mg tab fasted F/U BI 10mg sol fasted F/U BI 10mg tab fed	Date/time of BI 1467335 administration [REDACTED] days	Date/time of BI 1467335 administration in next period or End of trial (EOT) examination

\* For all defined study phases, the end date/time itself does not belong to the study phase

Vital signs will be presented for each assessment time point.

**CTP (Section 5.2.2.2 Adverse event collection and reporting):** [REDACTED]

*Therefore, all AEs which will occur throughout the treatment phases and the [REDACTED] REP will be considered as 'on treatment' (see [CTP] Section 7.3.3). Events which occur after the [REDACTED] REP and prior to the next drug administration will be considered as 'follow-up' events.*

Based on these definitions, two types of analyses will be provided in the report, as appropriate.

A) High-level analysis (for Section 15 and Appendix 16.1.9.2.8.2 &3 displays)

In these displays, the on treatment phase will be analysed (labelled with the name of the study treatment (short label)). The screening and follow-up periods will not be included.

For AE tables, a total over the active treatments ("Total BI 1467335") will be provided.

B) Low-level analysis (for Appendix 16.1.9.2.8.1 displays)

The separate phases, as defined in the table above, will be used in this analysis.

In addition, a total over the active treatments ("Total BI 1467335) and a total over all study phases ("Total overall") will be provided.

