			-0:30	07:30	High fat, high calorie breakfast (only in fed state - Treatment C)					
			0:00	08:00	Drug administration					
			0:15	08:15		x				
			0:30	08:30		x		x	x	
			0:45	08:45		x				
			1:00	09:00		x		x	x	x
			1:15	09:15		x				
			1:30	09:30		x				
			1:45	09:45		x				
			2:00	10:00	240 mL fluid intake	x		x	x	
			2:30	10:30		x				
			3:00	11:00		x				
			4:00	12:00	240 mL fluid intake, thereafter lunch ³	x				x
			6:00	14:00		x				
			8:00	16:00	Snack (voluntary) ³	x				
			10:00	18:00	Dinner ³	x				
		2	12:00	20:00		x	■	x	x	x
		24:00	08:00		Discharge from trial site, breakfast ³ (voluntary)	x	x	x	x	x
EOT	5	22-29			End of trial (EOT) examination ⁴	x		x	x	x

1. Subjects must be informed and written informed consent obtained prior to starting any screening procedures. Screening procedures include physical examination, check of vital signs, ECG, safety laboratory (including drug screening), demographics (including determination of body height and weight, smoking status and alcohol history), relevant medical history, concomitant therapy and review of inclusion/exclusion criteria. [REDACTED]
2. The time is approximate; the procedure is to be performed and completed within 3 h prior to drug administration
3. If several actions are indicated at the same time point, the intake of meals will be the last action
4. End of trial examination includes physical examination, body weight, vital signs, ECG, safety laboratory, recording of AEs and concomitant therapies
5. Only urine drug screening and alcohol breath test
6. AEs and concomitant therapies will be recorded throughout the trial, but will be specifically asked for at the time points indicated in the [Flow Chart](#) above
7. The time is approximate; the procedure is to be performed no later than 10 h prior to scheduled drug administration
8. Safety laboratory to be taken within 5 days prior to administration of study drug; in visits 3 and 4, only. AE and CT questioning to be done at this occasion.

TABLE OF CONTENTS

TITLE PAGE	1
CLINICAL TRIAL PROTOCOL SYNOPSIS	2
FLOW CHART	4
TABLE OF CONTENTS	5
ABBREVIATIONS	9
1. INTRODUCTION.....	12
1.1 MEDICAL BACKGROUND.....	12
1.2 DRUG PROFILE	12
2. RATIONALE, OBJECTIVES, AND BENEFIT - RISK ASSESSMENT	16
2.1 RATIONALE FOR PERFORMING THE TRIAL.....	16
2.2 TRIAL OBJECTIVES.....	16
2.3 BENEFIT - RISK ASSESSMENT	16
3. DESCRIPTION OF DESIGN AND TRIAL POPULATION.....	19
3.1 OVERALL TRIAL DESIGN AND PLAN	19
3.1.1 Administrative structure of the trial	19

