[REDACTED] (see [Section 2.1](#)), a preliminary REP is defined as [REDACTED] after administration of BI 1467335. Therefore, all AEs which will occur throughout the treatment phases and the preliminary REP will be considered as 'on treatment' (see [Section 7.3.3](#)). Events which occur after the preliminary REP and prior to the next drug administration will be considered as 'follow-up' events.

AE reporting to sponsor and reporting timelines

The Investigator must report SAEs, AESIs, and non-serious AEs which are relevant for the reported SAE or AESI, on the BI SAE form via fax immediately, within 24 hours of awareness, to the sponsor's unique entry point (country specific contact details will be provided in the ISF). The same timeline applies if follow-up information becomes available. On specific occasions the Investigator could inform the sponsor upfront via telephone. This does not replace the requirement to complete and fax the BI SAE form.

With receipt of any further information to these events, a follow-up SAE form has to be provided. For follow-up information, the same rules and timelines apply as for the initial information.

Information required

For each AE, the investigator should provide the information requested on appropriate CRF pages and the BI SAE form (if applicable).

The investigator should determine the causal relationship to the trial medication.

The following should also be recorded as an (S)AE in the CRF and on the SAE form (if applicable):

- Worsening of the underlying disease or of other pre-existing conditions

Proprietary confidential information © 2016 Boehringer Ingelheim International GmbH or one or more of its affiliated companies

- Changes in vital signs, ECG, physical examination and laboratory test results, if they are judged clinically relevant by the investigator

If such abnormalities have already pre-existed prior to trial inclusion, they will be considered as baseline conditions.

All (S)AEs, including those persisting after the individual subject's end of trial, must be followed up until they have been resolved, sufficiently characterised, or no further information can be obtained.

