7.3.3 Safety analyses

Safety will be assessed for the endpoints listed in [Section 5.2.1](#). All treated subjects (i.e., all subjects who received at least one dose of study drug), will be included in the safety analysis. Safety analyses will be descriptive and will be based on BI standards. No hypothesis testing is planned.

The analyses will be done by ‘treatment at onset’.

Treatments will be compared in a descriptive way. Tabulations of frequencies/proportions will be used for the evaluation of categorical (qualitative) data, and tabulations of descriptive statistics will be used to analyse continuous (quantitative) data.

Measurements (such as ECG, vital signs, or laboratory parameters) or AEs will be assigned to treatments (see [Section 4.1](#)) based on the actual treatment at the planned time of the measurement or on the recorded time of AE onset (concept of ‘treatment emergent AEs’).

Proprietary confidential information © 2016 Boehringer Ingelheim International GmbH or one or more of its affiliated companies

Therefore, all AEs which will occur throughout the treatment phase and the preliminary REP will be considered as 'on treatment'. Events which occurred after the preliminary REP will be considered as 'follow-up' events (refer to [Section 5.2.2.2](#)).

These assignments, including the corresponding time intervals, will be defined in detail in the TSAP.

Adverse events will be coded using the Medical Dictionary for Regulatory Activities (MedDRA). Frequency, severity and causal relationship of AEs will be tabulated by treatment, primary system organ class and preferred term. SAEs and other significant AEs (according to ICH E3), and AESIs will be listed separately (see [Section 5.2.2.1](#)).

Laboratory data will be compared to their reference ranges. Values outside the reference range as well as values defined as clinically relevant will be highlighted in the listings. Additionally, differences from baseline will be evaluated.

Vital signs or other safety-relevant data observed at screening, baseline, during the course of the trial and at the end-of-trial evaluation will be assessed with regard to possible changes compared to findings before start of treatment.

Relevant ECG findings will be reported as AEs.

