(ii) marked haematological and other lab abnormalities or lead to significant concomitant therapy as identified by the Clinical Monitor/Investigator at a Medical Quality Review Meeting.

The analysis of AEs will be based on the concept of treatment emergent AEs. That means that all adverse events occurring between first drug intake till last drug intake + residual effect period will be assigned to the randomised treatment. All adverse events occurring before first drug intake will be assigned to 'screening' and all adverse events occurring after the residual effect period will be assigned to "follow-up" (for listings only). For details on the treatments and the definition of study phases, see [Section 6.1](#).

An overall summary of AEs will be presented.

The frequency of subjects with AEs will be summarised by treatment, primary system organ class and preferred term. Separate tables will be provided for subjects with serious AEs, subjects with AESIs, and subjects with other significant AEs (according to ICH E3 ([5](#))). AEs which were considered by the investigator to be drug related will be summarised separately. AEs will also be summarised by maximum intensity. The system organ classes will be sorted

according to the standard sort order specified by the European Medicines Agency (EMA), preferred terms will be sorted by frequency (within system organ class).

Separate listings will be provided for all AEs, for serious AEs, for AESIs, for other significant AEs (according to ICH E3), for serious AEs, AESIs or other significant AEs, and for non-serious AEs that had an incidence of > 5% for at least one treatment.

The analysis of AEs will be based on the concept of treatment emergent AEs. For details on the treatments and the definition of study phases, see [Section 6.1](#).

An overall summary of AEs will be presented.

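### As written, SAP Table 6.1: 2 can leave an AE with onset at the end-of-trial (EOT) examination in no study phase, and so outside the low-level AE display and its Total overall column (minor)

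*SAP*

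**What the plan says.** SAP 6.1 defines the phases used to analyse AEs, laboratory data and vital signs: screening, one on-treatment phase per dose (dose to dose plus REP), and one follow-up phase per dose. A follow-up phase ends at "Date/time of BI 1467335 administration in next period or End of trial (EOT) examination". The footnote to the table adds: "For all defined study phases, the end date/time itself does not belong to the study phase".

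Two kinds of display follow. The high-level displays use the on-treatment phases only. For the low-level display in Appendix 16.1.9.2.8.1, "The separate phases, as defined in the table above, will be used in this analysis", with a total over the active treatments "and a total over all study phases", labelled Total overall.

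Elsewhere, follow-up has no upper limit. Protocol 7.3.3 says "Events which occurred after the preliminary REP will be considered as" follow-up, and leaves the detailed time intervals to the SAP. SAP 7.8.1 says "all adverse events occurring after the residual effect period will be assigned to" follow-up, but restricts this to listings and refers to SAP 6.1 for the phase definitions.

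**The concern.** A rule that excludes the end of every phase is harmless only where another phase begins at that moment. At EOT none does.

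Onsets at EOT are foreseeable. Footnote 4 of the protocol Flow Chart states: "End of trial examination includes physical examination, body weight, vital signs, ECG, safety laboratory, recording of AEs and concomitant therapies". Protocol 5.2.2.2 requires the following to be recorded as AEs: "Changes in vital signs, ECG, physical examination and laboratory test results, if they are judged clinically relevant by the investigator". The protocol names physical examination only at screening and EOT. Hormones, protein electrophoresis and urinalysis are also done only at those two visits (Protocol Table 5.2.3: 1, footnote). For these, EOT is the only scheduled assessment after dosing, so a new finding would naturally carry the EOT date.

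At stake is agreement between two parts of the same report: the AE listing would show the event as follow-up, while the appendix table and its grand total would not count it. ECG and physical-examination findings have no table or listing of their own (SAP 7.8.4 and 7.8.5.1), so the AE listing would be their only remaining place.

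**Working it through.** The plan gives no figure to reproduce. The check is whether the phases cover every moment up to and including EOT.

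**1. Boundaries.** Each phase is read as including its start and excluding its end (SAP 6.1, footnote).

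| Phase that ends | Ends at | Phase starting there | Moment covered? |
|---|---|---|---|
| Screening | First dose | On-treatment 1 | Yes |
| On-treatment (each) | Dose + REP | Follow-up (same dose) | Yes |
| Follow-up 1 and 2 | Next dose | Next on-treatment | Yes |
| Follow-up 3 | EOT examination | None | No |

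Only the last row leaves a gap.

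**2. Timing of EOT.** The Flow Chart puts EOT on Day 22 to 29, with dosing on Day 1. That is 22 - 1 = 21 to 29 - 1 = 28 days after the third dose.

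**3. Dependence on the REP.** The REP is redacted, so a range was tried: 1, 7, 14, 20, 21, 22, 28 and 29 days. Doses were set 21 days apart (the minimum washout) and EOT at 21 or 28 days after the third dose. An onset exactly at EOT is assigned as follows.

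| REP (days) | EOT at 21 days | EOT at 28 days |
|---|---|---|
| 1 to 21 | No phase | No phase |
| 22 and 28 | On-treatment 3 | No phase |
| 29 | On-treatment 3 | On-treatment 3 |

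So a REP of at most 21 days exposes all completers to the gap, a REP over 28 days exposes none, and in between it depends on the visit day. Protocol 5.2.2.2 foresees follow-up events between the REP and the next dose. With a 21-day minimum washout this suggests a REP of at most 21 days, but does not prove it.

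**4. Dependence on how the boundary is timed.** The table does not say which moment of the visit is meant.

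- Completion of the visit: findings made during it precede the boundary and fall in follow-up 3. No loss.
- Start of the visit: findings timed at or after the start have no phase.
- Calendar date: any onset on the EOT day has no phase.

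**5. Size.** AE tables count subjects, not events (SAP 7.8.1), and percentages use all subjects in the set (SAP 7). With the planned 18 subjects, one affected subject with no other AE in the row lowers Total overall in that row by 1/18 = 5.6 percentage points.

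**6. After the change.** With EOT included in the last follow-up phase, every case marked as having no phase in step 3 moves to follow-up 3. No other assignment changes.

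**The case against.** The strongest reply is that the intended assignment is already clear. Protocol 7.3.3 and SAP 7.8.1 both class AEs after the REP as follow-up without an upper limit, and a programmer would probably include the EOT visit. The restriction to listings in SAP 7.8.1 is weak evidence for dropping the event, because SAP 6.1 itself uses the follow-up phases in the low-level display. It may mean only that follow-up stays out of the main tables. SAP 7.8.1 also leaves further detail on AE summaries to a sponsor guideline that is not available here.

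Much of this stands. The intent is evident, and reading the boundary as completion of the visit removes the problem. The affected set is also narrow: sites record the time of onset, so a symptom mentioned at EOT that began on an earlier day stays in follow-up. But Protocol 7.3.3 hands the time intervals to the SAP, SAP 7.8.1 refers to SAP 6.1, and the footnote there excludes the end of every phase. The written rule therefore points the other way unless the EOT boundary is explained.

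A reader might infer that such an AE disappears from the report. The documents do not support that: the listing of all AEs in SAP 7.8.1 would carry it, as would the serious, AESI or other-significant listings where they apply. A reader might also assume an event rate and calculate how likely the table is to be wrong. The documents give no such rate. Nor would the result be the chance that Total overall changes, since that also requires the subject to have no other AE in the row.

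**Conclusion.** The point holds as a minor error in a definition. It rests on two conditions: EOT falls at or after the end of the redacted REP, and the boundary is read as the start or date of the visit. If both hold, an AE with onset at EOT is left out of one descriptive appendix display and its grand total, against the classification given elsewhere in the protocol and SAP. A subject who stops early and has EOT before the REP ends is still in the on-treatment phase and is not affected.

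The 5.6 points per affected subject and row assume 18 treated subjects. How many subjects would be affected cannot be derived from the documents.

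It would go too far to read this as a loss of EOT safety data or a threat to the safety conclusions. The high-level displays exclude follow-up by design. Laboratory and vital-sign values at EOT stay in the summaries over time and in the listings. The PK analysis does not use these phases.

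**What to change.** In SAP Table 6.1: 2, end the final follow-up phase after the EOT visit, for example at 00:00 on the day after EOT. Keep the exclusion of end times for all other phases, where it works.

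Also reconcile the table with SAP 7.8.1. Protocol 5.2.2.2 provides for relevant SAEs and AESIs to be reported after a subject's end of trial. Under SAP 7.8.1 those occurring after the REP are follow-up in the listings, but any with onset after EOT would have no phase in the table even once the EOT day is included. One sentence should say how such events are handled in the low-level display and in the listings.

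The cost is one table cell and one sentence, with a matching change to the phase derivation. No new data are needed, and the primary analysis and high-level safety displays stay as they are.
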